#### 4. ANALYSIS POPULATIONS

Population	Definition / Criteria	Analyses Evaluated
Screened	
 
All participants who were screened for eligibility
 
	
 
Study Population
 

Enrolled	
 
All participants who passed screening and entered the study.
 
Note screening failures (who never passed screening even if rescreened) and participants screened but never enrolled into the study (Reserve, Not Used) are excluded from the Enrolled population, as they did not enter the study.
 
	
 
Study Population
 

Safety	
 
All randomized participants who received at least one dose of study treatment.
 
This population will be based on the treatment the subject actually received for each respective cohort/period .
 
	
 
Study Population
 
Safety
 

Pharmacokinetic (PK) Concentration	
 
Part 1 (SAD) The PK Concentration Population will include all participants who undergo plasma PK sampling and have at least one evaluable concentration during the single dose phase of the study Part 1.
 
Part 2 (MAD) The PK Concentration Population will include all participants who undergo plasma PK sampling and have at least one evaluable concentration during the repeat dose phase of the study Part 2.
 
	
 
PK concentration Listing
 
PK individual concentration-time data plots
 

Pharmacokinetic (PK) Parameter	
 
Part 1 (SAD) The PK Parameter Population will include all participants who undergo plasma PK sampling and have evaluable PK parameters estimated during the single dose phase of the study Part 1.
 
Part 2 (MAD) The PK Parameter Population will include all
 
	
 
PK parameter listing
 
PK mean/median concentration-time data plots
 
PK parameter
 

Population	Definition / Criteria	Analyses Evaluated
	participants who undergo plasma PK sampling and have evaluable PK parameters estimated during the repeat dose phase of the study Part 2.	summary 
 
• Dose proportionality
 
• Accumulation ratio analysis and steady state analysis for Part 2
 

Refer to Appendix 12: List of Data Displays which details the population used for each display.

#### 4.1. Protocol Deviations

Important protocol deviations (including deviations related to study inclusion/exclusion criteria, conduct of the trial, patient management or patient assessment) will be summarised and listed.

Protocol deviations will be tracked by the study team throughout the conduct of the study, in accordance with the Protocol Deviation Management Plan Version 002 (09-May-2018).

- Data will be reviewed prior to freezing the database to ensure all important deviations are captured and categorised on the protocol deviations dataset.
- This dataset will be the basis for the summaries and listings of protocol deviations.

A separate listing of all inclusion/exclusion criteria deviations will also be provided. This listing will be based on data as recorded on the inclusion/exclusion page of the eCRF.

**5. CONSIDERATIONS FOR DATA ANALYSES AND DATA HANDLING CONVENTIONS**

**5.1. Study Treatment & Sub-group Display Descriptors**

Treatment Group Descriptions				
RandAll NG		Data Displays for Reporting		
Code	Description	Description	Header	Order in TLF
Part 1				
P/PS	Placebo/Placebo Sentinel	Placebo SD	SD PBO	9
D1/ D1S	GSK3640254 Dose Level 1/ GSK3640254 Dose Level 1 sentinel	GSK3640254 1 mg SD	SD 1mg	1
D2/ D2S	GSK3640254 Dose Level 2/ GSK3640254 Dose Level 2 sentinel	GSK3640254 3 mg SD	SD 3mg	2
D3/ D3S	GSK3640254 Dose Level 3/ GSK3640254 Dose Level 3 sentinel	GSK3640254 10 mg SD	SD 10mg	3
D4/ D4S	GSK3640254 Dose Level 4/ GSK3640254 Dose Level 4 sentinel	GSK3640254 30 mg SD	SD 30mg	4
D5/ D5S	GSK3640254 Dose Level 5/ GSK3640254 Dose Level 5 sentinel	GSK3640254 100 mg SD	SD 100mg	5
D6/ D6S	GSK3640254 Dose Level 6/ GSK3640254 Dose Level 6 sentinel	GSK3640254 200 mg SD	SD 200mg	6
D7/ D7S	GSK3640254 Dose Level 7/ GSK3640254 Dose Level 7 sentinel	GSK3640254 400 mg SD	SD 400mg	7
D8/ D8S	GSK3640254 Dose Level 8/ GSK3640254 Dose Level 8 sentinel	GSK3640254 700 mg SD	SD 700mg	8
Part 2				
RP	Placebo Repeated Dose	Placebo RD	RD PBO	5
R1	GSK3640254 Repeat Dose Level 1	GSK3640254 50 mg RD	RD 50mg	1
R2	GSK3640254 Repeat Dose Level 2	GSK3640254 100 mg RD	RD 100mg	2
R3	GSK3640254 Repeat Dose Level 3	GSK3640254 200 mg RD	RD200 mg	3
R4	GSK3640254 Repeat Dose Level 4	GSK3640254 320 mg RD	RD 320mg	4
R5	GSK3640254 Repeat Dose Level for Expansion Cohort	GSK3640254 200 mg RD	RD200 mg	3

**NOTES:**

- Order represents treatments being presented in TFL, as appropriate.
- Placebo is pooled by part

**5.2. Baseline Definitions**

For all endpoints (except as noted in baseline definitions) the baseline value will be the latest pre-dose assessment with a non-missing value, including those from unscheduled visits. If time is not collected, Day 1 assessments are assumed to be taken prior to first dose and used as baseline.

Parameter	Study Assessments Considered as Baseline				Baseline Used in Data Display
	Screening	Day -2	Day -1	Day 1 (Pre-Dose)	
Lab	X	X			Day -2 in each period
ECG	X	X	X	X	Day 1(Pre-Dose) in each period

Parameter	Study Assessments Considered as Baseline				Baseline Used in Data Display
	Screening	Day -2	Day -1	Day 1 (Pre-Dose)	
Vital Signs	X		X		Day -1 in each period

Unless otherwise stated, if baseline data is missing no derivation will be performed and baseline will be set to missing.

### 5.3. Other Considerations for Data Analyses and Data Handling Conventions

Other considerations for data analyses and data handling conventions are outlined in the appendices:

Section	Component
12.3	Appendix 3: Assessment Windows
12.4	Appendix 4: Study Phases and Treatment Emergent Adverse Events
12.5	Appendix 5: Data Display Standards & Handling Conventions
12.5	Appendix 6: Derived and Transformed Data
12.7	Appendix 7: Reporting Standards for Missing Data
12.8	Appendix 8: Values of Potential Clinical Importance

## 6. STUDY POPULATION ANALYSES

### 6.1. Overview of Planned Study Population Analyses

The study population analyses will be based on the Safety population, unless otherwise specified.

Study population analyses including analyses of subject's disposition, protocol deviations, demographic and baseline characteristics, prior and concomitant medications, and exposure and treatment compliance will be based on GSK Core Data Standards. Details of the planned displays are presented in Appendix 12: List of Data Displays.

Table 1 provides an overview of the planned study population analyses, with full details of data displays being presented in Appendix 12.

**Table 1 Overview of Planned Study Population Analyses**

Display Type	Data Displays Generated		
	Table	Figure	Listing
Subject Disposition			
Subject Disposition	Y		
Reasons for Screening Failures	Y		Y 
Study Treatment Discontinuation	Y		Y
Reasons for Subject Withdrawal			Y
Protocol Deviations			
Important  Protocol Deviations	Y		Y
Subjects with Inclusion/Exclusion Criteria Deviations			Y 
Populations Analysed			
Study Populations and Exclusions	Y		
Subjects Excluded from Any Population			Y
Subjects for whom the Treatment Blind was Broken			Y 
Demographic and Baseline Characteristics			
Demographic Characteristics	Y		Y
Race and Racial Combinations	Y		Y
Summary of Age Ranges	Y		
Concomitant Medications			
Concomitant Medications 	Y		Y
Exposure and Treatment Compliance			
Study Treatment Overall Compliance	Y		
Exposure to Study Treatment	Y		Y
Meal data			Y

**NOTES :**

- Y = Yes display generated.
- 1. Conditional displays, if data is available listing will be generated.
- 2. Listing of subjects excluded from any population will be generated only.
- 3. All protocol deviations will be listed, with important protocol deviations summarized.
- 4. Listing will be created for part 2 when data is available.
- 5. Provide summary table if more than 10 conmeds

## **6.2. Display Details**

### **6.2.1. Subject Disposition**

The disposition table will consist of all subjects in the safety population.

The number and percentage of subjects who failed screening and were, therefore, not entered into the study, overall and by reason, will be summarized. A listing of the screen failure record for all subjects who failed screening, including the reasons for screen failure will be produced.

Reasons for study treatment discontinuation will be summarized for each treatment group and overall. A by-subject listing of reasons for study withdrawal and a by-subject listing of reasons for study treatment discontinuation will be produced.

### **6.2.2. Protocol Deviations**

The number and percentage of subjects who had important protocol deviations defined in Section 4.1 will be summarized by treatment group and overall.

A listing of all protocol deviations will be produced.

Subjects with inclusion and exclusion deviations will be listed.

### **6.2.3. Populations Analysed**

The number of subjects who were enrolled into the study, and the number of subjects within each analysis population (Safety and PK) will be summarized for each treatment group and overall.

Subjects excluded from any population and subjects for whom the Treatment Blind was broken will be listed.

### **6.2.4. Demographic and Baseline Characteristics**

The demographic and baseline characteristics age, sex, race, ethnicity, height, weight, BMI will be summarized by treatment group and overall for the safety population. The count, mean, standard deviation, median, minimum, and maximum value will be computed for age, BMI, height, and weight.

A by-subject listing of demographic and baseline characteristics will also be produced.

Summaries of race and racial combinations will be produced for each treatment group and overall. A listing of race by subject will also be produced.

Summaries of age ranges will be produced for each treatment group and overall.

### **6.2.5. Concomitant Medications**

Medications will be coded using the GSK Drug v1.4 coding dictionary.

Concomitant medications will be summarised by GSK-Drug Anatomical Therapeutic Chemical (ATC) classification level 1 (body system) and ingredient if there are more than 10 concomitant medications. Drugs that are composed of a combination of ingredients will be displayed according to the ATC classifications of the ingredients, not of the combination. A by-subject listing will also be conducted.

#### **6.2.6. Exposure and Treatment Compliance**

The complete dosing experience will be listed for all subjects for both Part 1 and Part 2. The total duration of exposure (number of days on study drug), and cumulative dose will be summarized by treatment group for Part 2.

For subjects who completed the 14-day treatment period in Part 2 of the study, the expected number of doses is 14. For subjects who permanently discontinued the study treatment and/or withdrew from the study, the expected number of doses during the treatment period will be calculated using “Days on study drug” where “Days on study drug” is Last Dose Date – First Dose Date +1.

A summary of study medication compliance will be produced by treatment group for Part 2: 0%, >0-<100%, 100%, >100%. The compliance will be calculated for the whole study treatment period as the percentage of cumulative dose [ $100 * (\text{actual cumulative dose}) / (\text{expected cumulative dose for the subject's treatment duration})$ ]. For subjects who completed the 14-day treatment period in Part 2, the expected cumulative dose of GSK3640254 taken during the treatment period is as follows:

- For subjects who received 50 mg GSK3640254, the expected cumulative dose is 700 mg GSK3640254
- For subjects who received 100 mg GSK3640254, the expected cumulative dose is 1400 mg GSK3640254
- For subjects who received 200 mg GSK3640254, the expected cumulative dose is 2800 mg GSK3640254
- For subjects who received 320 mg GSK3640254, the expected cumulative dose is 4480 mg GSK3640254

For subjects who permanently discontinued study treatment or withdrew early from the study, the expected cumulative dose of GSK3640254 taken during the treatment period will be calculated as follows:

- For subjects who received 50 mg GSK3640254, the expected cumulative dose is  $50 \text{ mg} * (\text{Last Dose Date} - \text{First Dose Date} + 1)$
- For subjects who received 100 mg GSK3640254, the expected cumulative dose is  $100 \text{ mg} * (\text{Last Dose Date} - \text{First Dose Date} + 1)$
- For subjects who received 200 mg GSK3640254, the expected cumulative dose is  $200 \text{ mg} * (\text{Last Dose Date} - \text{First Dose Date} + 1)$

- For subjects who received 320 mg GSK3640254, the expected cumulative dose is 320 mg\*(Last Dose Date – First Dose Date +1)

The actual cumulative dose of GSK3640254 for all subjects is the sum of all doses, in mg, of study drug consumed for the duration of the study.

A by-participant listing of the meal data will also be generated including start and stop date and time of meal, dosing time, type of meal and whether the totality of the meal was ingested.

## 7. SAFETY ANALYSES

### 7.1. Overview of Planned Safety Analysis

The safety analyses will be based on the safety population, unless otherwise specified.

Safety data are the primary endpoints of the study, will be presented in tabular and summarized and listed descriptively accordingly to GSK's Integrated Data Standards Library (IDSL) standards. Details of the planned displays are presented in Appendix 12: List of Data Displays.

Table 2 provides an overview of the planned analyses, with further details of data displays being presented in Appendix 12.

**Table 2 Overview of Planned Safety Analyses**

Display Type	Absolute				Change from Baseline			
	Summary		Individual		Summary		Individual	
	T	F	F	L	T	F	F	L
Adverse Events (AEs)								
AEs Overview	Y							
All AEs				Y				
All Adverse Events by Maximum Grade and SOC and PT	Y							
All Drug-Related AEs				Y				
Drug-Related Adverse Events by Maximum Grade and SOC and PT	Y							
Serious AEs				Y				
Serious AEs by SOC and PT (Subjects & No. of Occurrences)	Y							
Drug Related Serious Adverse Events				Y				
Fatal AEs				Y				
Non-Fatal SAEs				Y				

Display Type	Absolute				Change from Baseline			
	Summary		Individual		Summary		Individual	
	T	F	F	L	T	F	F	L
Grade 2- 4 Adverse Events				Y				
AEs of Special Interest	Y			Y				
Adverse Events Leading to Withdrawal from Study/Permanent Discontinuation of Study Treatment	Y			Y				
Subject Numbers for Individual AEs				Y				
Common Adverse Events and Common Non-Serious Adverse Events By Overall Frequency	Y							
Relationship of Adverse Event System Organ Classes, Preferred Terms, and Verbatim Text				Y				
Laboratory Values								
Clinical Chemistry	Y			Y	Y			
Hematology	Y			Y	Y			
Urinalysis	Y			Y				
Clinical Chemistry Value of Potential Clinical Importance				Y				
Hematology Values of Potential Clinical Importance				Y				
Urinalysis Values of Potential Clinical Importance				Y				
Worst Case Chemistry Lab Results by Maximum Grade Post-Baseline Relative to Baseline	Y							
Worst Case Hematology Lab Results by Maximum Grade Post-Baseline Relative to Baseline	Y							
Worst Case Urine Lab Results by Maximum Grade Post-Baseline Relative to Baseline	Y							
Lab Results Identified				Y				

Display Type	Absolute				Change from Baseline			
	Summary		Individual		Summary		Individual	
	T	F	F	L	T	F	F	L
as Adverse Events								
Treatment Emergent Laboratory Toxicities	Y							
Subjects with grades 2 or higher laboratory toxicities				Y				
ECG								
ECG Findings	Y			Y				
Abnormal ECG Findings				Y				
ECG Values	Y				Y			
All ECG Values for Subjects with a Value of PCI				Y				
Maximum Increase in QTc Values Post-Baseline Relative to Baseline by Category					Y			
Mean (95% CI) Change from Baseline in QTc interval by Time and Treatment						Y		
Vital Signs								
Vital Values	Y			Y	Y			
All Vital Signs for Subjects with Values of PCI				Y				
Hepatobiliary (Liver)								
Liver Monitoring/Stopping Event Reporting	Y							
Summary of Hepatobiliary Laboratory Abnormalities	Y							

**NOTES :**

- T = Table, F = Figure, L = Listing, Y = Yes display generated, PCI = Potential Clinical Importance
- Summary = Represents TFL related to any summaries (i.e. descriptive statistics) of the observed raw data.
- Individual = Represents FL related to any displays of individual subject observed raw data.

**7.2. Display Details****7.2.1. Adverse Events Analysis**

All adverse event (AE) data will be summarized, sorted by the system organ class and preferred term assigned by MedDRA version 21.0, and presented by treatment group. The following summaries will be provided:

- Adverse events overview
- All adverse events by maximum grade and SOC and PT
- Drug related adverse events by maximum grade and SOC and PT
- Serious adverse events by SOC and PT (Subjects & No. of Occurrences)
- Adverse events of Special Interest
- Adverse events leading to withdrawal from study/permanent discontinuation of study treatment
- Common ( $\geq 5\%$ ) adverse events by overall frequency
- Common ( $\geq 5\%$ ) non-serious adverse events by overall frequency

The following listings will be provided:

- All adverse events
- Drug related adverse events
- Serious adverse events
- Drug related serious adverse events
- Fatal adverse events
- Non-fatal serious adverse events
- Grade 2 - 4 Adverse Events
- Adverse events of special interest
- Adverse events leading to withdrawal from study/permanent discontinuation of study treatment
- Subject Numbers for Individual AEs
- Relationship of Adverse Event System Organ Classes, Preferred Terms, and Verbatim Text

#### **Adverse Events of Special Interest:**

A comprehensive list of MedDRA terms based on clinical review will be used to identify each type of GI event (Nausea and Vomiting, Dyspepsia etc.). [Changes to the MedDRA dictionary may occur between the start of the study and the time of reporting and/or emerging data from on-going studies may highlight additional adverse events of special interest, therefore the list of terms to be used for each event of interest and the specific events of interest will be based on the safety review team (SRT) agreements in place at the time of reporting.]

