	Headache	1		1	2	2	2	2	
	Parasthesia			1					
	Migraine			1					
Gastrointestinal Disorders	Vomiting					2			
	Feces Soft	1							
	Diarrhea			1	1	2			1
	Abdominal Pain				1				
	Feces Discolored					1			
	Feces Pale							1	
Infections and Infestations	Nasopharyngitis			1		1		1	
	Oral Herpes				1				
	Viral Infection			1		1			
	Upper Respiratory Tract Infection						1		
Respiratory, Thoracic, and Mediastinal Disorders	Nasal Obstruction			2					1
	Cough			1		1			
	Oropharyngeal Pain							1	
	Hemoptysis							1	
Skin and Subcutaneous Disorders	Contact Dermatitis	1	1	1			1	1	

SOC	PT	AEs by Blinded SAD Cohort/Period							
		1 m g	3 m g	10 mg	30 mg	100 mg	200 mg	400 mg	700 mg
Psychiatric Disorders	Depression	1							
	Insomnia	1							
	Nightmare		1						1
Injury, Poisoning, and Procedural Complications	Face Injury	1							
	Skin Abrasion						1		
	Contusion			1					
	Limb Injury	1							
General Disorders and Administration Site Conditions	Catheter site pain			1					
	Vessel Puncture Site Bruise		1						
	Chest Pain	1							
Investigations	Transaminases Increased						1		1
Musculoskeletal and Connective Tissue Disorders	Musculoskeletal Pain				1				
Total AEs by Blinded SAD Cohort/Period		9	4	13	6	10	6	7	5

Table 2 Summary Table (all AEs) in blinded MAD 50 – 200 mg doses

SOC	PT	AEs by Blinded MAD Cohort/Period		
		50 mg	100 mg	200 mg
Nervous System Disorders	Dizziness	1	2	3
	Headache	4	2	5
	Somnolence	1		
	Disturbance in Attention			2
	Lethargy			2
	Dizziness Postural			1
	Hypoaesthesia			1
	Dysgeusia			1
Gastrointestinal Disorders	Lip Dry	1		
	Mouth Ulceration	1		

SOC	PT	AEs by Blinded MAD Cohort/Period		
		50 mg	100 mg	200 mg
	Aphthous Ulcer	1		
	Abdominal Pain	1		1
	Abdominal Distention		1	1
	Glossodynia			1
	Constipation			2
	Nausea			1
	Gastroesophageal Reflux Disease			1
General Disorders and Administration Site Conditions	Catheter site pain			1
	Vessel Puncture Site Bruise		1	1
	Fatigue	2	2	1
	Feeling Cold	1		
	Catheter site Bruise			1
Skin and Subcutaneous Disorders	Contact Dermatitis	1		2
	Blister		1	
	Dry Skin		1	
	Rash			1
	Rash Maculopapular			1
	Pruitis			1
Musculoskeletal and Connective Tissue Disorders	Back pain	1	1	2
	Musculoskeletal Stiffness	1		
	Muscle Twitching		1	
Injury, Poisoning, and Procedural Complications	Laceration			1
	Contusion	1	1	2
Infections and Infestations	Hordeolum		1	
	Abscess		1	
	Oral Herpes			1
Psychiatric Disorders	Agitation		1	
	Abnormal Dreams			1
	Nightmare		1	

SOC	PT	AEs by Blinded MAD Cohort/Period		

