Part 2 also includes an Expansion Cohort which was conducted at the conclusion of Cohort 5. VH's prior and structurally similar MI (GSK3532795) ceased development in Phase 2b (due in part to a higher proportion of participants experiencing GI intolerability). GSK3532795, studied in Phase 1 studies of normal healthy volunteers showed diarrhoea of up to 65%. The Expansion Cohort will evaluate the rate of GI intolerability in 24 participants (active/PBO =18/6). The dose studied (200 mg) was previously studied doses in the MAD and did not meet safety or PK stopping criteria. While no formal statistical testing will be performed, a summary of GI AEs will be provided from: 1) 24 participants receiving one of the GSK3640254 doses studied

previously and 2) 14 participants receiving placebo across the entire MAD. These numbers of participants should provide sufficient clinical inference and better estimation of GI AEs frequency at a given dose (which can be used to inform subsequent dose selection/therapeutic index for HIV-1 infected participants).

Participants in both Part 1 and Part 2 will have a screening visit within 30 days prior to first dose and a follow-up visit 7-14 days after the last dose. Maximum duration of study participation will be approximately 12 weeks.

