- When an AE/SAE occurs, it is the responsibility of the investigator to review all documentation (eg, hospital progress notes, laboratory, and diagnostics reports) related to the event.
- The investigator will then record all relevant AE/SAE information in the CRF.
- It is **not** acceptable for the investigator to send photocopies of the participant's medical records to GSK in lieu of completion of the GSK /AE/SAE CRF page.
- There may be instances when copies of medical records for certain cases are requested by GSK. In this case, all participant identifiers, with the exception of the participant number, will be redacted on the copies of the medical records before submission to GSK.
- The investigator will attempt to establish a diagnosis of the event based on signs, symptoms, and/or other clinical information. Whenever possible, the diagnosis (not the individual signs/symptoms) will be documented as the AE/SAE.

Assessment of Intensity

The investigator will make an assessment of intensity for each AE and SAE reported during the study using the DAIDS grading table (http://rsc.tech-res.com/docs/default-source/safety/daids_ae_grading_table_v2_nov2014.pdf) and assign it to 1 of the following categories:

- Mild: no or minimal interference with usual social & functional activities
- Moderate: greater than minimal interference with usual social & functional activities
- Severe: inability to perform usual social & functional activities. An AE that is assessed as severe should not be confused with an SAE. Severe is a category utilized for rating the intensity of an event; and both AE and SAE can be assessed as severe.
- Life Threatening: inability to perform basic self-care functions

An event is defined as 'serious' when it meets at least 1 of the predefined outcomes as described in the definition of an SAE, NOT when it is rated as severe.

Assessment of Causality

- The investigator is obligated to assess the relationship between study treatment and each occurrence of each AE/SAE.
- A "reasonable possibility" of a relationship conveys that there are facts, evidence, and/or arguments to suggest a causal relationship, rather than a relationship cannot be ruled out.
- The investigator will use clinical judgment to determine the relationship.
- Alternative causes, such as underlying disease(s), concomitant therapy, and other risk factors, as well as the temporal relationship of the event to study treatment administration will be considered and investigated.

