### 11.6.3. Safety

Adverse Events

 
Gastrointestinal nonspecific symptoms and therapeutic procedures
 

Abdominal discomfort

Abdominal distension
Abdominal pain
Abdominal pain lower
Abdominal pain upper
Abdominal symptom
Abdominal tenderness
Abnormal faeces
Aerophagia
Anorectal discomfort
Bowel movement irregularity
Change of bowel habit
Constipation
Defaecation disorder
Defaecation urgency
Diarrhoea
Discoloured vomit
Epigastric discomfort
Eructation
Faecal volume decreased
Faecal volume increased
Faeces hard
Faeces soft
Flatulence
Frequent bowel movements
Gastrointestinal pain
Gastrointestinal sounds abnormal
Gastrointestinal toxicity
Infrequent bowel movements
Nausea
Non-cardiac chest pain
Oesophageal discomfort
Oesophageal pain
Vomiting
Anorectal swelling
Antacid therapy
Antidiarrhoeal supportive care
Antiemetic supportive care
Breath odour
Chest pain
Colonic lavage
Dysphagia
Early satiety
Gastritis prophylaxis
Gastrointestinal disorder therapy

Gastrointestinal tract irritation
Gastrooesophageal reflux prophylaxis
Glycogenic acanthosis
Hypovolaemia
Laxative supportive care
Malabsorption
Mucous stools
Pernicious anaemia
Post procedural constipation
Post procedural diarrhoea
Post-tussive vomiting
Probiotic therapy
Procedural nausea
Procedural vomiting
Prophylaxis against diarrhoea
Prophylaxis of nausea and vomiting
Regurgitation
Retching
Steatorrhoea
Vomiting projectile

ECG Parameters
RR Interval

 
IF RR interval (msec) is not provided directly, then RR can be derived as :             
 
[1] If QTcB is machine read & QTcF is not provided, then :                 <math display="block">RR = \left[ \left( \frac{QT}{QTcB} \right)^2 \right] * 1000</math> 
 
[2] If QTcF is machine read and QTcB is not provided, then:                 <math display="block">RR = \left[ \left( \frac{QT}{QTcF} \right)^3 \right] * 1000</math> 
 
 
 
If ECGs are manually read, the RR value preceding the measurement QT interval should be a collected value THEN do not derive.
 

Corrected QT Intervals

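### The only GI term list printed in the SAP lacks Dyspepsia and reflux disease, and the on-treatment and treatment-emergent date rules disagree; both points are minor

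*SAP*

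**What the plan says.** **Term list.** SAP 7.2.1, Adverse Events of Special Interest, states: "A comprehensive list of MedDRA terms based on clinical review will be used to identify each type of GI event (Nausea and Vomiting, Dyspepsia etc". It adds that the terms and the specific events "will be based on the safety review team (SRT) agreements in place at the time of reporting". It does not cite 11.6.3. The one GI term list printed in the SAP is in 11.6.3, headed "Gastrointestinal nonspecific symptoms and therapeutic procedures". Its only reflux entry is "Gastrooesophageal reflux prophylaxis". Protocol 3.2.2, Table 2, tabulates one event of "Gastroesophageal Reflux Disease", in the 200 mg column. On recording, protocol Appendix 4 says: "Whenever possible, the diagnosis (not the individual signs/symptoms) will be documented as the AE/SAE".

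**Date rules.** SAP 11.4.1 defines three phases:
- Pre-Treatment: dates up to and including the first treatment start date.
- On-Treatment: later dates, up to the last stop date plus 5 days.
- Post-Treatment: anything after that.

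SAP 11.4.2 flags an AE as treatment emergent from the start date through the stop date, both inclusive. SAP 11.7.2.1 moves certain AEs with a missing start day to the treatment start date and calls them On-treatment, citing Appendix 4, which is where 11.4.1 and 11.4.2 sit.

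**The concern.** A list meant to identify each type of GI event should contain the term for a type that the same SAP names. Symptom terms are an imperfect substitute, because the protocol prefers the diagnosis to be recorded. A programmer looking in the SAP for the terms behind Tables 3.5 and 3.32 would find only the 11.6.3 list.

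This matters because the Expansion Cohort was run to evaluate GI intolerability, and the protocol promises that "a summary of GI AEs will be provided from: 1) 24 participants receiving one of the GSK3640254 doses studied" previously, set against 14 on placebo. A special-interest table that drops upper-GI diagnoses would show fewer GI events than the all-AE table.

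On dates, one day cannot be both Pre-Treatment and On-treatment under the same appendix. The different end points also leave some AEs On-Treatment but not treatment emergent, with no stated reason.

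**Working it through.** **1. Check that the reflux event belongs to the 200 mg column.** The column total printed in protocol Table 2 is 43. Re-adding by system organ class: nervous 15 + GI 7 + general 4 + skin 5 + musculoskeletal 2 + injury 3 + infections 1 + psychiatric 1 + ear 2 + renal 2 + cardiac 1 = 43. The total is reproduced with the reflux event included.

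**2. Match tabulated GI events to the 11.6.3 list.** The list has 65 terms. Matching is by exact term, with US and UK spellings treated as the same. Counts are blinded events, not participants.

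| MAD dose | GI-class events | On the list | Not on the list |
|---|---|---|---|
| 50 mg | 4 | 1 | lip dry, mouth ulceration, aphthous ulcer |
| 100 mg | 1 | 1 | none |
| 200 mg | 7 | 5 | glossodynia, reflux disease |
| Total | 12 | 7 | 5 |

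Four of the five misses are oral complaints. Without them the list catches 7 of 8 events overall and 5 of 6 at 200 mg. The one non-oral miss is reflux disease; adding that term gives 6 of 6 non-oral events at 200 mg. Adding Dyspepsia changes no count so far, because protocol Tables 1 and 2 show no dyspepsia event.

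In the SAD (protocol Table 1), the GI events are vomiting 2 + soft faeces 1 + diarrhoea 5 + abdominal pain 1 + discoloured faeces 1 + pale faeces 1 = 11. The list catches 2 + 1 + 5 + 1 = 9 and misses the discoloured and pale faeces.

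**3. Check how far symptom terms cover dyspepsia.** Protocol 9.4.6, Table 10, gives early satiety, bloating and belching as its symptoms. The list has Early satiety, Abdominal distension and Eructation, so all three are covered if bloating and belching are coded that way. Of the six atypical symptoms in that table, chest pain and abdominal pain are listed; pharyngitis, asthma, bronchitis and hoarseness are not. The main gap is therefore the diagnosis itself.

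**4. Apply the two date rules to Part 2** (start Day 1, stop Day 14).

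| Onset | 11.4.1 phase | 11.4.2 flag |
|---|---|---|
| Day 1 | Pre-Treatment | treatment emergent |
| Days 2–14 | On-Treatment | treatment emergent |
| Days 15–19 | On-Treatment | not treatment emergent |
| Day 20 on | Post-Treatment | not treatment emergent |

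- On-Treatment covers Days 2 to 19, which is 18 days.
- Treatment emergent covers Days 1 to 14, which is 14 days.
- They share Days 2 to 14, which is 13 days, and differ on 1 + 5 = 6 days.

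In Part 1, using the first start date and the last stop date as 11.4.1 words it, the rules differ on the first dosing date and on the five days after the last single dose.

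**5. Find where a date rule could bite.** No AE display is stated to use either rule. SAP 7.2.2, however, labels one laboratory summary on-treatment and another treatment emergent, and 11.4.2 defines the latter for AEs only. Part 2 laboratory tests are scheduled on Days 16 and 18. Those days are inside the 11.4.1 window, and would be outside the 11.4.2 window if that rule were borrowed. No scheduled Part 2 laboratory test falls on Day 1.

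**The case against.** **Term list.** SAP 7.2.1 does not say that 11.6.3 is the special-interest list, and the 11.6.3 heading covers only nonspecific symptoms and therapeutic procedures. The final terms rest with the safety review team. That stands, and it makes the omission conditional. It does not remove the point: the reasons 7.2.1 gives for later change are dictionary updates and additional events from emerging data, and Dyspepsia is neither, since it is already named.

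A reader might infer that the GI intolerability rate will be understated. The documents do not support that. Abdominal pain and diarrhoea, the complaints the protocol stresses, are both listed. Table 3.29 shows every AE by class and term. The arm coded as "GSK3640254 Repeat Dose Level for Expansion Cohort" shares the 200 mg header with Cohort 5, giving 6 + 18 = 24 participants. Placebo is pooled by part, giving 4 × 2 + 6 = 14. The promised GI summary can be drawn from that table. The reflux event is preliminary and blinded.

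**Date rules.** A study phase and an AE flag may differ by design, so the five-day tail alone could be intended, though the SAP does not say so. A note under 11.4.2 asks that clock times be considered where collected, which eases the Day 1 clash for AEs. It does not help an onset imputed to the start date, nor the end-date difference.

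A reader might also infer that AEs are lost, or that the two windows never overlap in a Part 1 period. Neither is supported. The all-AE tables are not stated to filter on either rule. The lack of overlap needs a per-period reading that the first-start, last-stop wording of 11.4.1 only partly allows. The dose-to-next-dose rule in 11.4.3 assigns AEs to periods and is not in dispute.

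**Conclusion.** Both points hold and both are minor.

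1. The printed GI list lacks the diagnosis term for an event type the SAP names, and lacks reflux disease. If it is used as printed, Tables 3.5 and 3.32 and Listings 20 and 61 would omit such diagnoses, while Tables 3.2 and 3.29 would keep them. On the data in the protocol the effect, oral complaints aside, is one event in the MAD, possibly in a placebo participant. This rests on exact-term matching and on the list being used unamended, which the SAP neither states nor rules out.

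2. The date rules contradict each other on the first dosing date and differ over the five days after the last dose. An AE starting the day after the last dose, in either part, is On-Treatment but not treatment emergent. The practical exposure is in the laboratory displays that carry those labels without a stated rule. No loss of AEs from the all-AE tables is claimed.

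**What to change.** Before database freeze:

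- Add Dyspepsia, Gastrooesophageal reflux disease and related upper-GI diagnosis terms to the 11.6.3 list. State in 7.2.1 that the final list agreed by the safety review team is the one behind Tables 3.5 and 3.32.
- Reconcile 11.4.1, 11.4.2 and 11.7.2.1 so that both windows start at first dosing and end at the same point after the last dose. State which rule the on-treatment and treatment-emergent laboratory displays use.

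The cost is text edits to the SAP. No new table and no new data collection is needed.
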